3.3.3 Handling of Unscheduled Visits

Visits that fall outside the visit windows defined in the CSP will be classified as Unscheduled Visits. Unscheduled visits will be numbered sequentially with an increment of 0.1. For example, if two measurements are done in an unscheduled visit that occurs between Day 3 and Day 8, then these visits will be numbered UNS 2.1 and 2.2 in the order they occurred.

The values measured at unscheduled visits will not be included in the by-visit summary tables, they will be included in the overall summary tables (for abnormalities, minimum/maxima etc.) and will be presented in the listings.

3.3.4 Multiplicity/Multiple Comparisons

Not applicable.

3.3.5 Handling of Protocol Deviations in Study Analysis

Important protocol deviations (IPD) are defined as those deviations from the protocol likely to have an impact on the perceived efficacy and/or safety of study treatments. The impact of IPDs on the safety results will be investigated by assessing the robustness of the study results and conclusions to the choice of analysis set, both including and excluding data potentially affected by IPDs.

This estimation will be performed on a Data Review Meeting (DRM) shortly before database lock. Results and population assignments will be summarized in a DRM report which will be signed off by all relevant scientific experts.

The list of all IPDs is provided in the AstraZeneca Non-compliance Handling Plan (NHP). The IPD are classified per the AstraZeneca NHP. Refer to this document for all details about protocol deviations. Relevant IPDs used to exclude subject from the sensitivity analysis 1 (section 4.2.1.5) are reported below:

- All IPDs included in the category 1 - Inclusion Criteria Deviations (Subject who did not meet the below criteria. Those who entered the study even though they did not satisfy the entry criteria. If Screen failure, then this is not a protocol deviation).
- All IPDs included in the category 2 - Exclusion Criteria Deviations (Enrolled, even though subject fulfilled the below criteria. Those who entered the study even though they did not satisfy the entry criteria. If Screen failure, then this is not a protocol deviation).

- All IPDs included in the category 3 - Discontinuation Criteria for study product met but patient not withdrawn from study treatment.
- All IPDs included in the category 5 - Investigational Product (IP) Deviation, with the exception of the IPD 5.02 - Subjects who were randomised but did not receive IP which is not considered relevant.
- All IPDs included in the category 6 - Excluded Medications taken.

4 STATISTICAL ANALYSIS

This section provides information on definitions, derivation, and analysis/data presentation per domain.

4.1 Study Population

The domain study population covers subject disposition, analysis sets, protocol deviations, demographics, baseline characteristics medical history, prior and concomitant medication, and study drug compliance.

4.1.1 Subject Disposition and Completion Status

4.1.1.1 Definitions and Derivations

Not applicable.

4.1.1.2 Presentation

Subject disposition will be summarized based on the Enrolled Set and will include the following information:

- Number of subjects enrolled.
- Number of subjects randomized,
- Number and percentage of subjects who received at least one dose of study drug,
- Number of subjects not randomized.
- Number and percentage of subjects who completed treatment/discontinued treatment (including reasons for IP discontinuation).
- Number and percentage of subjects who completed or discontinued study (including reason for early withdrawal).

Summaries will be by treatment group and overall. Percentages will be calculated using "Subjects randomized" as denominator. A randomization listing will be presented and will include the following information: randomization number, full enrolment number, date of randomization and randomized treatment group.

Subjects affected by the COVID-19 pandemic and subjects with reported issues in the Clinical Trial Management System due to COVID-19 pandemic will be listed.

4.1.2 Analysis Sets

4.1.2.1 Definitions and Derivations

Analysis sets are defined in Section 3.2.

4.1.2.2 Presentation

Analysis sets will be summarized based on the Enrolled Set. The number of subjects included and excluded (including reason for exclusion) in each analysis population will be presented by treatment group.

4.1.3 Protocol Deviations

4.1.3.1 Definitions and Derivations

Important protocol deviations (IPDs) will be defined in the NHP (refer to Section 3.3.5) and are considered as those deviations from the protocol likely to have an impact on the perceived efficacy or safety of study treatment. The final list of IPDs will be determined before each DBL.

4.1.3.2 Presentation

IPDs will be summarized based on the Randomized set. The number and percentage of subjects meeting each IPD criterion will be summarized by treatment group. Subjects who deviate from a given criterion more than once will be counted once for that criterion. Any subjects with more than one IPD will be counted once in the overall summary.

4.1.4 Demographics

4.1.4.1 Definitions and Derivations

Age is measured in years and calculated as:

$$\text{Age (years)} = (\text{Date of randomization} - \text{date of birth} + 1) / 365.25$$

4.1.4.2 Presentation

Demographics (age, sex, ethnicity, race) will be summarized based on the Full Analysis Set. Summaries will be presented by treatment group and according to the principles outlined in Section 3.3.

4.1.5 Baseline Characteristics

4.1.5.1 Definitions and Derivations

Body mass index (BMI) is calculated as:

$$\text{BMI (kg/m}^2\text{)} = \text{weight (kg) / height}^2 \text{ (m)}$$

4.1.5.2 Presentation

Baseline characteristics (height, weight, BMI, nicotine use and alcohol use) will be summarized based on the Full Analysis Set. Summaries will be presented by treatment group and according to the principles outlined in Section 3.3.

4.1.6 Disease Characteristics

4.1.6.1 Definitions and Derivations

Disease characteristics are defined as the following lipid related parameters measured at baseline:

- LDL-C with reflex to PUC/beta-Quantification equals to:
 - LDL-C derived by Friedewald formula if LDL-C (Friedewald) $\geq 40\text{mg/dL}$ and Triglycerides (TG) $< 400\text{mg/dL}$.
 - LDL-C (PUC/beta-Quantification) if LDL-C (Friedewald) $< 40\text{mg/dL}$ or TG $\geq 400\text{mg/dL}$.
- LDL-C derived by Friedewald formula, without reflex, LDL-C derived by Martin/Hopkins formula and Direct LDL-C.
- HDL-C and Non-HDL-C.
- VLDL-C.
- ApoA1 and ApoB.
- Lipoprotein(a) (Lp(a)).
- Triglycerides (TG).

- Remnant cholesterol

4.1.6.2 Presentation

Disease characteristics will be summarized based on the Full Analysis set. Summaries will be presented by treatment group and according to the principles outlined in Section 3.3.

4.1.7 Medical History and Concomitant Disease

4.1.7.1 Definitions and Derivations

Medical/surgical history, and concomitant (called “current”) diseases are coded using MedDRA version 24.0 or higher. The imputation method described in Section 3.3.1.2 will be used in the instance that partial or missing dates are recorded. After imputation of dates, current diseases will be classified as prior (called “past”) or current.

A past disease is defined as any disease with a start and end date prior to the first dose date (exclusive). A current disease is defined as any disease with an end date on or after the first dose date. A disease with a completely missing end date will be considered as current.

4.1.7.2 Presentation

Medical/surgical history, and current diseases will be summarized based on the Full Analysis Set. The number and percentage of subjects with relevant medical/surgical history/current diseases will be presented by treatment group and summarized by System Organ Class (SOC) and Preferred Term (PT). Subjects with histories in more than one SOC/PT will be counted only once in that SOC/PT. Tables will be sorted alphabetically by SOC and PT.

4.1.8 Prior and Concomitant Medications

4.1.8.1 Definitions and Derivations

Prior (called “past”) and concomitant (called “current”) medications are coded using the WHO-DD. The imputation method described in Section 3.3.1.2 will be used in the instance that partial or missing dates are recorded.

Past medications are defined as those that stopped and started prior to the first dose date. All medications on or after the first dose date are considered as current, this includes those medications that started prior to date of first dose but continued after.

4.1.8.2 Presentation

Past and current medications will be summarized based on the Full Analysis Set. The number and percentage of subjects will be presented by treatment group and summarized by Anatomical Therapeutic Chemical (ATC) Class and Preferred Term (PT). Subjects with medications in more than one ATC class/PT will be counted only once in that ATC class/PT. Tables will be sorted alphabetically by ATC class and PT.

4.1.9 Study Drug Compliance

4.1.9.1 Definitions and Derivations

Treatment compliance will be calculated for each subject and expressed as a percentage. The percent treatment compliance will be calculated as the number of doses received relative to the expected number of doses.

$$\text{Treatment compliance (\%)} = 100 \times \frac{\text{Number of doses received}}{\text{Expected number of doses}}$$

4.1.9.2 Presentation

Treatment compliance will be summarized based on the Safety Analysis Set and by treatment group, using the principles outlined in Section 3.3 for continuous variables.

4.2 Endpoint Analyses

This section covers details related to the endpoint analyses such as primary, secondary, safety, and exploratory endpoints including sensitivity and supportive analyses.

Statistical category	Endpoint	Population	Intercurrent event strategy	Population level summary (analysis)	Details in section
Objective 1: To assess the effect of different doses of AZD8233 on LDL-C versus placebo.					
Primary	Absolute change from baseline in log-transformed LDL-C in serum	Full analysis set.	The hypothetical estimand strategy will be used for the primary outcomes, therefore all subjects are assumed to have completed treatment without intercurrent events.	Mean difference in change between treatments (LSMD) at week 12	4.2.1
Objective 2: To assess the effect of different doses of AZD8233 on PCSK9 versus placebo.					
Secondary	Absolute change from baseline in log-transformed PCSK9 in plasma.	Full analysis set.	Included in the analysis regardless of	Mean difference in change	4.2.2

Statistical category	Endpoint	Population	Intercurrent event strategy	Population level summary (analysis)	Details in section
	Percent change from baseline in PCSK9 in plasma.		treatment discontinuation	between treatments (LSMD) at week 12	
Objective 3: To assess the effect of different doses of AZD8233 on LDL-C versus placebo.					
Secondary	Percent change from baseline in levels of LDL-C in serum	Full analysis set.	Included in the analysis regardless of treatment discontinuation	Mean difference in change between treatments (LSMD) at week 12	4.2.3
Objective 4: To assess the effect of AZD8233 on other lipid parameters versus placebo.					
Secondary	Levels of other lipid parameters	Full analysis set.	Included in the analysis regardless of treatment discontinuation	Mean difference in change between treatments (LSMD) at week 12	4.2.4
Objective 5: To evaluate PK of AZD8233.					
Secondary	Population PK parameters	PK analysis set		NA	4.2.5
Objective 6: To evaluate the immunogenicity of AZD8233.					
Secondary	Development of antidrug antibodies (ADA) and ADA titer (if subjects are ADA positive) during treatment and follow-up.	Safety analysis set		NA	4.2.6
Objective 7: To assess the safety and tolerability of AZD8233.					
Safety	Adverse Events	Safety analysis set		NA	4.3.2
	Injection site reactions			NA	4.2.7
	Clinical laboratory examinations.			NA	4.3.3, 4.3.4, 4.3.5
	Vital signs, ECG.			NA	4.3.6, 4.3.7

Statistical category	Endpoint	Population	Intercurrent event strategy	Population level summary (analysis)	Details in section
Objective 8: To collect and store blood (plasma) and urine samples for potential future exploratory research aimed at exploring biomarkers involved in PK, PD, safety (including antiplatelet antibodies) and tolerability related to AZD8233 treatment or cardiometabolic diseases.					
Exploratory	Evaluation of changes in biomarkers. Results of potential future exploratory biomarker research may be reported outside this study's CSR.	Full analysis set.		NA	

4.2.1 Primary Endpoint

The primary estimand is the hypothetical estimand, assuming all the participants had continued treatment until Week 12 without experiencing an intercurrent event. The primary analysis will be carried out with likelihood based repeated measures model, which will provide an unbiased treatment effect under the assumption of Missing At Random.

4.2.1.1 Definition

The primary efficacy endpoint is change from baseline in log-transformed LDL-C at the end of Week 12.

LDL-C with reflex to PUC/beta-Quantification will be used as the primary LDL-C variable for evaluation, this equates to:

- LDL-C derived by Friedewald formula if LDL-C (Friedewald) \geq 40mg/dL and TG $<$ 400mg/dL
- LDL-C (PUC/beta-Quantification) if LDL-C (Friedewald) $<$ 40mg/dL or TG \geq 400mg/dL.

LDL-C derived by the Friedewald formula without reflex, LDL-C derived by the Martin/Hopkins formula and direct LDL-C will also be presented as a supplementary analysis.

4.2.1.2 Derivations

LDL-C values will be assigned to analysis visits as defined in Section 3.3.2. Measurements below the LLOQ for which the exact value cannot be determined will be replaced by the LLOQ divided by the square root of 2.

Change from baseline of the log-transformed variable will be calculated as the visit value in the natural logarithm minus the baseline value in natural logarithm.

Percent change will be derived from the MMRM estimates as:

$$\text{Mean percent change} = 100 * (\exp(\text{LSMean}) - 1)$$

4.2.1.3 Handling of Dropouts and Missing Data

Missing data will not be imputed and only observed values will be reported in the summary tables and listings. Treatment discontinuation visit will be mapped according to Section 3.3.2.

4.2.1.4 Primary Analysis of Primary Endpoint

The analysis and presentation will be based on subjects in the Full Analysis Set.

The study hypothesis to be tested is treatment effect of AZD8233 across different dose levels [REDACTED] compared to placebo. The null hypotheses for these tests are that the absolute change in log-transformed LDL-C for AZD8233 at some dose level is equal to the absolute change in log-transformed LDL-C for placebo.

A mixed model with repeated measures will be fitted using the log-transformed LDL-C data. The model will include the log-transformed LDL-C baseline value as a covariate and time point (visit number), treatment, and the interaction between time point and treatment will be included as factors. The response variable will be change from baseline in log-transformed LDL-C. The model will be fitted with an unstructured covariance structure, and the Kenward-Roger correction applied to obtain the degrees of freedom. The primary model will include data up to and including Week 12 as a response variable.

Estimation of the treatment effect will be calculated for each visit after baseline and presented alongside the corresponding 95% confidence interval. In case of issues when fitting the model to the data, the following hierarchical model fitting procedure will be adopted:

1. The MMRM will be fitted using a spatial power covariance structure; Visit will be expressed as scheduled visit days to accomplish the variance-covariance matrix estimation.
2. The MMRM will be fitted using a compound symmetry covariance structure.
3. An ANCOVA model for Week 12 only will be used.

Comparisons of the change from baseline between the treatment groups will be conducted using the least square mean difference (LSMD) between treatment groups as estimated by

the fitted model. Pair-wise comparisons will be done for each AZD8233 dose [REDACTED] vs. placebo. In addition, pair-wise comparisons between AZD8233 dose groups [REDACTED] will also be done for reference. The p-value for each comparison will be presented alongside the LSMD and its 95% CI. In addition, LSMs and 95% CIs will be back-transformed to present as relative (geometric) difference among treatment groups and the relative change will also be presented as the percent change from baseline.

Change from baseline will be summarized by visit and treatment groups using descriptive statistics (arithmetic mean, SD, minimum, median, maximum) and based on the principles defined in Section 3.3.

The plots over the visits will be created by the treatment groups for the following cases:

- Mean (SD) for absolute value over time.
- Geometric LSMean (95% CI) based on MMRM estimates.

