3.3.2 Visit Window

Study visits windows are defined in the table below:

	Screening		Treatment Period							EDV	Follow-up period ^a	Final Follow-up Visit ^b
Visit Number	1	2	3	4	5	6	7	8	9		10, 11, 12, 13, 14, 15	16
Study Week			0	1	3	4	6	8	10		12, 14, 16, 18, 20, 22	24
Study Day	Days -28 to -10	Days -7 to -4	Day 1	Day 8	Day 22	Day 29	Day 43	Day 57	Day 71		Days 85, 99, 113, 127, 141, 155	Day 169
Visit Window				± 1 day	± 2 days		± 2 days	± 2 days				

Analysis Visit Windows

Analysis visit windows will be defined for the lipid parameters, ECG, anti-AZD8233 antibodies, laboratory results and vital signs which summarize values by visit. These analysis visit windows will be exhaustive so that data recorded at any time point has the potential to be summarized. Inclusion within the window will be based on the actual date and not the intended date of visit.

Analysis visit windows will be constructed such that the upper limit of the window intervals fall halfway between two scheduled visits, where the number of days between visits is odd, the additional day will be applied to the lower interval of the later date.

Table 1: Analysis visit windows for lipid parameters, laboratory parameters* and vital signs

Analysis Visits	Scheduled visit day	Analysis visit window (days)
Baseline ^a	Day -28 to Day 1	≤ Day 1
Treatment period		
Day 1	Day 1	Day 1 ^b
Week 1	Day 8	Day 2 – Day 14
Week 3	Day 22	Day 15 – Day 25
Week 4	Day 29	Day 26 – Day 35
Week 6	Day 43	Day 36 – Day 49
Week 8	Day 57	Day 50 – Day 63
Week 10	Day 71	Day 64 – Day 77
Follow-up period		

Week 12	Day 85	Day 78 – Day 91
Week 14	Day 99	Day 92 – Day 105
Week 16	Day 113	Day 106 – Day 119
Week 18	Day 127	Day 120 – Day 133
Week 20	Day 141	Day 134 – Day 147
Week 22	Day 155	Day 148 – Day 161
Week 24	Day 169	Day 162 onwards.

*Complement activation panel is collected pre-dose on Visits 12, 3, 6 and 8 only. Hs-CRP is collected at Visit 1, 8 and all follow-up visits.

^a Baseline is defined as the last measurement prior to first dose of study treatment. Pre-dose values on Day 1 qualify as baseline measurements.

^b Day 1 is defined as date of first dose of study treatment. Includes all measurements collected at Day 1 after the first dose of IP.

Table 2: Analysis visit windows for ECG

Analysis Visits	Scheduled visit day	Analysis visit window (days)
Baseline ^a	Day -28 to Day 1	≤ Day 1
Treatment period		
Day 1	Day 1	Day 1 ^b
Week 1	Day 8	Day 2 – Day 18
Week 4	Day 29	Day 19 – Day 42
Week 8	Day 57	Day 43 – Day 70

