Follow-up period		
Week 12	Day 85	Day 71 – Day 91
Week 14	Day 99	Day 92 – Day 112
Week 18	Day 127	Day 113 – Day 140
Week 22	Day 155	Day 141 onwards

^a Baseline is defined as the last measurement prior to first dose of study treatment. Pre-dose values on Day 1 qualify as baseline measurements.

^b Day 1 is defined as date of first dose of study treatment. Includes all measurements collected at Day 1 after the first dose of IP.

Table 3: Analysis visit windows for anti AZD8233 antibodies

Analysis Visits	Scheduled visit day	Analysis visit window (days)
Baseline ^a	Day -28 to Day 1	≤ Day 1
Treatment period		
Day 1	Day 1	Day 1 ^b
Week 1	Day 8	Day 2 – Day 18
Week 4	Day 29	Day 19 – Day 42
Week 8	Day 57	Day 43 – Day 70
Follow-up period		
Week 12	Day 85	Day 71 – Day 98
Week 16	Day 113	Day 99 – Day 126
Week 20	Day 141	Day 127 – Day 154
Week 24	Day 169	Day 155 onwards.

^a Baseline is defined as the last measurement prior to first dose of study treatment. Pre-dose values on Day 1 qualify as baseline measurements.

^b Day 1 is defined as date of first dose of study treatment. Includes all measurements collected at Day 1 after the first dose of IP.

An early discontinuation visit (EDV) may take place at any point during the study up to Week 12. In this instance, follow-up visits (Week 2, Week 4 etc.) will begin at date of last administered treatment and performed every 2 weeks after last dose prior to study discontinuation. For those patients with an early discontinuation, an additional analysis visit window will be applied to follow-up visits as follows and will be used for the summary of safety and lab data.

If there is more than one value per subject within an analysis visit window then the closest value to the scheduled visit date will be summarized, or the later value if the values are equidistant from the nominal visit date, the remaining visits will be treated as ‘Unscheduled Visits’ Listings will display all values contributing to a time point for a subject and will highlight the value that contributed to the summary table where feasible.

For summaries showing the maximum or minimum values, the maximum/minimum value recorded on treatment will be used, regardless of where it falls in an interval. For summaries

at a subject level (i.e., the maximum) all values will be included regardless of whether they appear in a corresponding visit-based summary.

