4.2.3.3 Handling of Dropouts and Missing Data

Refer to Sections 4.2.1.3.

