4.2.3.4 Analysis of Secondary Endpoint

LDL-C will be analyzed using the statistical model described for the primary endpoint (refer to Section 4.2.1.4).

LDL-C endpoints will be summarized by visit and treatment group using descriptive statistics (arithmetic mean, SD, minimum, median, maximum) using the principles defined in Section 3.3.

The plot of LSMean (95% CI) based on the MMRM estimates will be produced.

Percent change from baseline for direct LDL-C will be analysed similarly.

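### Part B: no rule keeps LDL-C measured after treatment discontinuation out of the primary MMRM, although the primary estimand is hypothetical

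*SAP*

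**What the plan says.** SAP Part B 4.2.1 defines the primary estimand as hypothetical, "assuming all the participants had continued treatment until Week 12 without experiencing an intercurrent event". Protocol 9.4.1 and the endpoint table in SAP Part B 4.2 agree. The analysis is a likelihood-based MMRM, justified under missing at random (MAR).

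The rules that decide which values enter that model are these:

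- SAP Part B 4.2.1.4 uses the full analysis set, and "The primary model will include data up to and including Week 12 as a response variable".
- SAP Part B 4.2.1.3: "Treatment discontinuation visit will be mapped according to Section 3.3.2".
- SAP Part B 3.3.2 assigns samples by actual date: "These analysis visit windows will be exhaustive so that data recorded at any time point has the potential to be summarized".
- For early discontinuers, 3.3.2 adds a further window that "will be used for the summary of safety and lab data".

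The endpoint table gives the secondary LDL-C and PCSK9 endpoints a different strategy: "Included in the analysis regardless of treatment discontinuation". For secondary LDL-C, the dropout rule in 4.2.3.3 reads in full "Refer to Sections 4.2.1.3", and 4.2.3.4 says "LDL-C will be analyzed using the statistical model described for the primary endpoint". PCSK9 (4.2.2.4) uses that model too.

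**The concern.** An MMRM targets the effect under continued treatment only if values observed after the intercurrent event are removed first. MAR is an assumption about values that are missing. It does nothing for values that were observed off treatment.

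As written, discontinuers who stop attending are handled as if they had continued, while those who keep attending contribute off-treatment LDL-C. The result is neither the hypothetical estimand nor a clean treatment-policy one. If LDL-C drifts back towards baseline off drug, the estimated reduction is diluted. The hypothetical and regardless-of-discontinuation labels also have no different data rule behind them, so at least one label is wrong. Part B is meant to size the effect and support dose selection (Protocol 4.2), so the estimate matters more here than the p-value.

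**Working it through.** **Would the values exist?** Protocol 7.1 (Part B) asks participants who discontinue treatment to return at their original visits for three months. Protocol Table 2, footnote n, gives visits every 2 weeks after the last dose. LDL-C is scheduled at the early discontinuation visit and at all follow-up visits. Two-weekly visits after a last dose on Day 1 fall on Days 15, 29, 43, 57, 71 and 85; after a last dose on Day 29, on Days 43, 57, 71 and 85. Both schedules therefore reach Day 85 (Week 12). Someone who stops after the Day 57 dose has had all three doses, so only those who miss Day 29 or Day 57 matter.

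**How far off treatment are they?** At Day 85 they are 84 or 56 days past the last dose, against 28 days on schedule. Take the half-life h of 2 to 3 weeks (Protocol 4.2) and simple exponential decline. Relative exposure is the sum of 2^(−(85−d)/h) over doses received, divided by the same sum over Days 1, 29 and 57.

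- h = 14 days: terms 0.016, 0.063 and 0.250, total 0.328. Stopped after dose 2: 0.078/0.328 = 0.24. Stopped after dose 1: 0.016/0.328 = 0.05.
- h = 21 days: terms 0.063, 0.157 and 0.397, total 0.617. Stopped after dose 2: 0.220/0.617 = 0.36. Stopped after dose 1: 0.063/0.617 = 0.10.

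This is plasma exposure. The LDL-C effect retained need not follow it.

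**The plan's own figures.** Protocol 9.2 gives log SD 0.3, differences 0.693 and 0.33, 18 evaluable per arm, two-sided 5% and 10% drop-out. By noncentral t with 34 degrees of freedom, power is above 99.99% for 0.693 (stated: more than 95%) and 89.4% for 0.33 (stated: about 89%). 18/0.9 = 20 per arm, 60 in total. These reproduce. With 20 per arm, power for 0.33 is 92.4%.

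**Dilution.** Assume k of 20 active participants are off treatment but measured at Week 12 and have lost a fraction f of their effect. Estimated reduction = 1 − exp(−0.693 × (1 − (k/20) × f)).

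For the dose comparison, assume log effects 0.693 and 1.023 and the same k and f in both arms. Power comes from 200,000 simulated trials per case (pooled two-sided t-test, 20 per arm).

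| k | f | Estimated reduction | Dose difference 0.33 × (1 − kf/20) | Dose-comparison power |
|---|---|---|---|---|
| 0 | – | 50.0% | 0.330 | 92% |
| 1 | 0.5 | 49.1% | 0.322 | 89% |
| 1 | 1 | 48.2% | 0.314 | 81% |
| 2 | 0.5 | 48.2% | 0.314 | 86% |
| 2 | 1 | 46.4% | 0.297 | 66% |

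Power against placebo is at least 99.99% in every case. Dose-comparison power falls by more than the smaller difference alone implies, because mixing on- and off-treatment values inflates the within-arm variance. Shrinking the mean only, at 10% off treatment and 20 per arm, gives 86.2% to 89.6%.

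**Do the sensitivity analyses deal with it?** Analysis 1 in SAP Part B 4.2.1.5 excludes whole participants who are not per-protocol completers, including their on-treatment data. Analysis 2 imputes missing values only, and is considered only above 20% missing. Neither changes the primary estimate.

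**The case against.** The intent can be inferred. The endpoint table contrasts a hypothetical primary with secondaries that ignore discontinuation, and Protocol 9.4.1 names continued treatment to Week 12. On that reading one operational sentence is missing. This stands as evidence of intent, but it gives no rule and no cut-off, and the written rules lead to inclusion.

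SAP Part B 3.3.2 says an additional window for discontinuers follows, and none is visible in the text available; a table may have been lost in extraction. LDL-C might also count as lab data, since Protocol Table 7 lists it among laboratory assessments. Against this, the window is stated to serve summaries of safety and lab data, Table 1 of the SAP lists lipids separately from laboratory parameters, and a window assigns visits without excluding values.

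Mapping the discontinuation visit is often harmless, because that visit will usually fall within 28 days of the last dose. This is correct. The problem lies in the later visits, where attendance is voluntary.

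The upper end of the size is strained. Protocol 2.2 mentions 4 treatment discontinuations among more than 120 exposed, about 3%, not stated to be complete. At 4/120 the shrinkage is 0.6 to 1.2 points for half or all effect lost. The chance of 2 or more of 20 stopping in both active arms is then about 2%, before requiring attendance at Week 12. Losing the whole effect also sits awkwardly with 24% to 36% exposure remaining after dose 2. The 66% figure is therefore an extreme case, and it concerns a comparison made only for reference.

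**Conclusion.** The concern holds. Followed literally, the Part B primary analysis does not estimate its stated estimand: no text in the protocol or SAP removes LDL-C observed after treatment discontinuation, and the written rules bring it in. The direction is towards placebo if LDL-C returns towards baseline off drug.

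The documents do not fix the size. With 1 or 2 of 20 active participants affected, both the count and the effect lost being assumptions, a 50% reduction is understated by 0.9 to 3.6 percentage points. The tests against placebo are essentially unaffected. What suffers is the size of the estimate and the reference comparison between doses. This should be corrected, but it does not threaten the main conclusion of efficacy.

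**What to change.** In SAP Part B 4.2.1.4, add:

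> Intercurrent events for the primary estimand are discontinuation of study treatment, a missed scheduled dose (Day 29 or Day 57), and [any others, for example a change in background LDL-lowering medication]. LDL-C values collected after an intercurrent event (for a stopped or missed dose, after the day that dose was due) are set to missing before the primary MMRM is fitted.

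In 3.3.2, state whether discontinuers' lipid samples are windowed by study day from Day 1 or re-anchored to the last dose. In 4.2.1.6, report the MMRM on all observed data as a supplementary treatment-policy analysis.

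The cost is one paragraph and one programming flag; sensitivity analysis 2 already has to identify visits whose preceding dose was missed. A few observations leave the primary model, which then relies on MAR for them. If these participants fall within the planned 10%, 18 per arm still contribute (20 × 0.9). That is the number used for sizing, with 89% power for the dose comparison and above 99.9% against placebo.
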